4.3 Subject Disposition

Subject disposition information will be summarized for each treatment sequence and for each treatment group. Counts (number and percent) of patients who are randomized, who receive the trial medication, who complete the trial, and who withdraw from the trial will be presented by treatment sequence and by treatment group. The reasons for early withdrawals will also be tabulated. The randomized patients within each treatment group will be used as the denominator for the percentage calculation. Subject disposition (including the number of screened patients and the reason for screen failure), inclusion / exclusion criteria, and comments will be listed.

The number and percent of patients in each analysis population will also be tabulated.

4.4 Demographics and Baseline Characteristics

Demographics and baseline characteristics will be summarized descriptively by treatment sequence and by treatment group for the Safety Analysis Set and repeated for the Full Analysis Set and Per Protocol Set if they are different from the Safety Analysis Set.

Demographic and baseline characteristics include, but are not limited to, age at informed consent, gender, race, ethnicity, body weight, and body mass index (BMI). Continuous

variables (e.g., age, weight, and BMI) will be summarized by descriptive statistics (n, mean, SD, minimum, median, and maximum). Categorical variables (e.g., gender, race, and ethnicity) will be summarized by the number and percentage of patients in corresponding categories.

Medical history will be summarized for the number and percentage of patients for each system organ class and preferred term by treatment group and in total. Medical and social history will also be listed.

4.5 Prior and Concomitant Medications

All medications administered during the trial will be listed and coded using the most current version of the World Health Organization (WHO) Drug Dictionary. A listing of all concomitant medications including the reported term, preferred term, and Anatomical Therapeutic Chemical (ATC) class, start and stop dates, and other relevant data will be provided. The number and percentage of patients taking prior and concomitant medications will be summarized by treatment group, ATC, and preferred term. Concomitant medications include all medications taken during the trial from screening onward. Prior medications include all medications taken and discontinued before screening.

4.6 Primary Endpoint Analyses

All safety analyses will be performed using the Safety Analysis Set. Safety variables will be summarized using descriptive statistics for continuous variables and frequency and percentage for categorical variables. These safety analyses will be compared qualitatively between the two treatment groups.

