3. TRIAL OVERVIEW

3.1 Overall Trial Design and Treatment Assignment

[figure not shown]
This is a Phase 2 single-center, open-label, 2-part, randomized cross-over trial in adult patients (≥ 18 years of age) with T1DM. Patients who already manage their T1DM using continuous subcutaneous (SC) insulin infusion pump therapy will be enrolled. The trial will assess the safety and efficacy of the BP, using either the iLet or the iPhone platform, using the glucagon analog

ZP4207 versus Lilly glucagon. In Part 1, up to 10 patients will participate in two 1-day treatment arms in random order (iPhone-based BP using ZP4207 and iPhone-based BP using Lilly glucagon) according to the randomization scheme. In Part 2, up to 10 new patients will participate in two 1-day treatment arms in random order (iLet using ZP4207 and iLet using Lilly glucagon) according to the randomization scheme. The BP will also administer insulin (insulin lispro, Lilly Humalog) using the same blood glucose (BG) control algorithm for all 4 treatment arms. The trial will be conducted at the Massachusetts General Hospital (MGH) Diabetes Center in Boston, MA. Up to 40 patients will be enrolled in this trial with the expectation that up to 10 patients will complete each part of the trial.

[figure not shown]
The overall trial design is displayed in Figure 1.

Figure 1. Trial Design Schematic

Part 1:

Part 2:

Patients can only participate in 1 part of the trial.
 ADA = anti-drug antibodies, BP = bionic pancreas.

Patients who have completed the Screening Visit and meet all of the inclusion and none of the exclusion criteria will be enrolled. The order of the treatment visits will be randomized in blocks of 2 patients.

The schedule of events for the trial is provided in Table 1.

Table 1. SCHEDULE OF PROCEDURES – PARTS 1 AND 2

Trial Visit	Visit 1 [1] Screening	Visit 2 Training	Visit 3 [2] [3] [4] [5] (1 st Treatment Visit)	Visit 4 [2] [3] [5] (2 nd Treatment Visit)	Visit 5 ADA Assessment Visit [6]	Visit 6 Follow-Up [7]
Informed consent	X					
Assess/confirm eligibility	X	X				
Demographics	X					
Medical, surgical, and social history; allergies	X					
Concomitant illness	X					
Concomitant medications	X	X	X	X	X	X
Height, weight, physical examination, and vital signs including body temperature and blood pressure [8]	X		X [9]	X [9]		
12-lead ECG	X		X [10]	X [10]		
Urine HCG pregnancy test and menstrual history [11]	X		X	X		
FSH [12]	X					

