4. STATISTICAL METHODOLOGY

4.1 Baseline, Endpoint, and Other Statistical Considerations

The clinical statistical analyses will be performed by Medpace.

Descriptive summary statistics including number (n), mean, median, standard deviation (SD), and range (minimum, maximum) for continuous variables (interquartile range [25th, 75th percentile] for non-parametric tests), and counts and percentages for categorical variables will be used to summarize data, as appropriate. Where appropriate, p-values will be reported. All statistical tests will be conducted using 2-sided tests with 5% significance level and 95% confidence interval, unless otherwise stated.

For all analyses, the 2 treatment arms from Part 1 (iPhone-based BP) will be compared, and the 2 treatment arms from Part 2 (iLet) will be compared. The analyses of Part 1 will be completely separate from the analyses of Part 2.

All data will be listed in patient-level data listings.

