4.6.8 Pain and Nausea

Pain and nausea will be summarized descriptively by treatment and visit time point (i.e., start of visit, hourly, and end of visit). Change from the start of the visit will also be summarized by treatment group. Individual data will be listed.

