4.7.1 Bionic Pancreas Function Endpoints

The plasma ZP4207/Lilly glucagon concentration will be summarized descriptively at each time point by treatment group (e.g. n, mean, SD, coefficient of variation [CV%], median, minimum, and maximum). Mean concentration will be plotted over time, by treatment group. Individual plasma concentration-time curves will be plotted by patient.

The analysis of BP function endpoints will be on an intention-to-treat basis. In cases where a treatment arm was not completed (and that arm was not repeated according to protocol criteria), available data from that arm will be used in the data analysis.

A paired t-test or the Wilcoxon signed rank test for comparison of means with normally or non-normally distributed residuals, respectively, will be used. The Shapiro-Wilk test will be used to determine the normality of the residuals for each comparison. The residuals will be obtained from an ANOVA model with treatment group as the fixed effect. If the p-value of the test is less than 0.001, the non-parametric method will be utilized to analyze the endpoint parameter. The sample SAS code for the paired t-test analysis involving the average percent of insulin dose amounts successfully delivered by the pump is included here:

```
.....  
Note: InsTrt1 = the average percent of insulin dose amount successfully  
delivered by the pump during treatment with Lilly glucagon.  
InsTrt2 = the average percent of insulin dose amount successfully  
delivered by the pump during treatment with ZP4207.  
.....  
proc ttest ;  
paired InsTrt1*InsTrt2;  
run;
```

In a secondary analysis, any period effect and any interaction between treatment and period will be looked for, although no such interaction is predicted for the efficacy outcomes. The efficacy outcomes will be analyzed using a mixed model including terms for treatment and period as fixed effects, an interaction term, and subject nested within sequence as a random effect. A patient must have a data value for both periods in order to be included in the analysis for the given parameter. The sample SAS code for this analysis is included here:

```
.....  
Note: Insulin = the average percent of insulin dose amounts successfully  
delivered by the pump  
subject = subject identification number.  
sequence = sequence order (1=glucagon/ZP4207, 2=ZP4207/glucagon).  
treatment = treatment group (1=Lilly glucagon, 2=ZP4207).  
period = analysis period number (1=Visit 3, 2=Visit 4).  
.....
```

```

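### Nausea and pain VAS, components of the primary endpoint, are compared only from by-treatment summaries, so the precision of the within-patient ZP4207-minus-glucagon difference is not reported

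*SAP*

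**What the plan says.** Section 3.1 gives the design: "This is a Phase 2 single-center, open-label, 2-part, randomized cross-over trial in adult patients". It continues: "In Part 1, up to 10 patients will participate in two 1-day treatment arms in random order". Part 2 repeats this with up to 10 new patients. Section 4.1 keeps the parts apart: "The analyses of Part 1 will be completely separate from the analyses of Part 2".

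Section 3.2.1 lists nausea and pain, each on a 10 cm VAS, among the components of the primary endpoint. Section 4.6 sets the rule for comparing all safety variables: "These safety analyses will be compared qualitatively between the two treatment groups". Section 4.6.8 specifies the two scales: "Pain and nausea will be summarized descriptively by treatment and visit time point (i.e., start of visit, hourly, and end of visit"). It then adds: "Change from the start of the visit will also be summarized by treatment group". Individual data are also listed.

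For the device-function endpoints, section 4.7.1 does use the pairing: "A paired t-test or the Wilcoxon signed rank test for comparison of means with normally or non-normally distributed residuals, respectively, will be used". It also gives a mixed model with period and with subject within sequence. Section 4.7.2 carries a similar analysis over to plasma glucose. Neither is carried over to the safety variables.

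**The concern.** A cross-over lets each patient serve as their own control. The change score in 4.6.8 is taken within one visit. It removes the patient's level at the start of that visit but does not compare the two drugs within the patient. The tables will show a mean and SD for each drug, and those figures do not determine the SD of the within-patient difference. A reader of the summary tables cannot tell whether a given mean difference reflects a consistent shift in nearly every patient or a mixture of large changes in both directions.

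This matters because section 5 describes the aim as exploring the safety of ZP4207 relative to Lilly glucagon, so the comparison is of interest. With the parts analysed separately, each comparison rests on about 10 pairs. Any remark in the study report that the drugs were similar, or different, on nausea or pain would have no planned interval behind it.

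**Working it through.** The SAP has no figure to reproduce. Section 5 states that the sample size was not formally calculated, and no SD, effect size or correlation is given. The calculations below are illustrations.

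**Inputs.** n = 10 pairs per part (section 3.1, upper limit). 95% intervals (the general level in section 4.1). Equal SD of the VAS measure under the two drugs (assumed). Within-patient correlation ρ (assumed, shown over a range).

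**Half-widths, in units of the VAS SD.**

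- Two columns read as independent groups: t(0.975, 18) × √(2/10) = 2.101 × 0.447 = 0.94.
- Paired: t(0.975, 9) × √(2(1−ρ)/10), with t(0.975, 9) = 2.262.

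| ρ (assumed) | √(2(1−ρ)/10) | Paired half-width | Ratio to 0.94 |
|---|---|---|---|
| 0 | 0.447 | 1.01 | 1.08 |
| 0.3 | 0.374 | 0.85 | 0.90 |
| 0.5 | 0.316 | 0.72 | 0.76 |
| 0.7 | 0.245 | 0.55 | 0.59 |
| 0.9 | 0.141 | 0.32 | 0.34 |

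The two half-widths are equal when 1−ρ = (2.101/2.262)² = 0.86, that is at ρ of about 0.14. Below that, pairing costs a little because it has 9 rather than 18 degrees of freedom. Above it, the paired interval is narrower: by 10%, 24% and 41% at ρ = 0.3, 0.5 and 0.7. With 8 or 12 pairs the pattern is the same.

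**What group summaries leave open.** Take an invented set of 10 values for one drug, in cm: 0, 0, 0.5, 0.5, 1, 1.5, 2, 2.5, 3, 4. For the other drug take 1.2, 0.8, 1.6, 1.4, 2.3, 2.2, 3.2, 3.3, 4.1, 4.9. The means are 1.5 and 2.5 and the SDs 1.35 and 1.34, however the values are matched to patients.

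- Matched in the order shown: SD of the differences 0.205, half-width 2.262 × 0.205/√10 = 0.15, mean difference 1.0 with 95% CI 0.85 to 1.15. All 10 patients are higher on the second drug.
- Matched with the second list reversed: SD of the differences 2.62, half-width 2.262 × 2.62/√10 = 1.88, mean difference 1.0 with 95% CI −0.88 to 2.88. Six of 10 are higher.

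The by-treatment means and SDs are the same in both cases. Only the paired SD, or the individual pairs, separates them.

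**The case against.** Descriptive safety reporting is usual in a small Phase 2 trial without a formal sample size, and section 4.6 states that choice openly. The primary objective in section 2.1.1 names no comparison with glucagon. This stands: the plan is inefficient here, not wrong in its figures.

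Several stronger readings are tempting, but the SAP does not support them:

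- *The within-patient difference is never estimated.* For patients with both visits, the mean paired difference equals the difference of the two treatment means, which can be taken from the planned summaries. What is missing is its SD or interval.
- *A consistent rise would be hidden.* Sections 4.1 and 4.6.8 provide patient-level listings. With up to 10 patients per part, a reader could pair the values by hand. The two invented datasets would look different there. A listing is still not a planned estimate, and pairing by hand afterwards leaves the choice of VAS summary open in an open-label trial.
- *Section 4.6 contradicts section 4.1.* Section 4.1 says "For all analyses, the 2 treatment arms from Part 1 (iPhone-based BP) will be compared", and likewise for Part 2. A qualitative comparison is still a comparison, so there is no conflict.
- *The primary endpoint is treated worse than every secondary endpoint.* The non-glycemic endpoints in section 4.7.3 are also only described.
- *The plan loses a stated amount of precision.* No independent-groups interval is planned, so 0.94 SD is a benchmark and not a planned output. The change scores already remove each visit's starting level, so their correlation between visits may be lower than that of raw scores, and the gain smaller.

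**Conclusion.** The point holds as a cheap improvement, limited to nausea and pain VAS. The planned outputs allow the point difference to be derived but do not report its precision, although the design supplies the pairs and section 4.7.1 already uses them for device function. At 10 pairs, the effect on the 95% half-width runs from about 8% wider at zero correlation to 41% narrower at 0.7, compared with reading the columns as independent groups. This assumes equal SDs and roughly normal differences. The correlation is assumed throughout, so the size of the gain is not established. The case for the change does not depend on a large gain, because at present no interval is planned at all.

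A reader might extend the argument to vital signs and ECG intervals. That would add many intervals at about 10 pairs each in two separate parts, and it is not recommended.

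**What to change.** Keep the hourly summaries in section 4.6.8 and add text on these lines:

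*Separately for each part, and for patients with data in both periods, the within-patient difference (ZP4207 minus Lilly glucagon) in the mean change from visit start and in the peak change from visit start will be presented for nausea VAS and for pain VAS, each with a 95% confidence interval and a display of the individual paired values. These results are descriptive; no hypothesis test is planned.*

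The peak is included because averaging over the visit could dilute a brief episode.

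The cost is SAP wording and one extra table with its paired display, from data already collected. It yields 2 scales × 2 summaries × 2 parts = 8 descriptive intervals, each on about 10 pairs. VAS scores may be skewed, so the individual paired values should be read alongside each interval. The simple difference is not adjusted for period. Randomisation in blocks of 2 should keep the two orders close to balanced, so a period effect would largely cancel from the mean difference, though it would add to the SD.

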4.6.1 Adverse Events

All AEs from the time of signing the informed consent through trial completion will be recorded on the electronic Case Report Form (eCRF). An AE is any untoward medical occurrence in a clinical trial patient administered an IMP and which does not necessarily have a causal relationship with the treatment. An AE can, therefore, be any unfavorable and unintended sign (e.g., and abnormal laboratory finding), symptom, or disease temporarily associated with the use of an IMP, whether or not considered related to the IMP. For this trial, insulin (insulin lispro, Lilly Humalog), glucagon (glucagon for inject, Eli Lilly), and ZP4207 are all regarded as IMP.

Adverse events will be coded using the latest version of the Medical Dictionary for Regulatory Activities (MedDRA). The actual used version number will be documented in the database. Individual AEs will be presented in a listing including relationship to trial product/device, severity, and treatment period at onset. If more than 20 treatment-emergent AEs (AEs with onset after [first] dosing at Visit 3 until the follow-up Visit 6) are registered, a summary table including number of AEs, number of patients with at least 1 AE, and percentage of exposed patients with at least 1 AE will be made by system organ class and treatment period at onset. Specific by-patient listings of serious adverse events (SAEs) and treatment-emergent AEs leading to discontinuation will be provided.

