
1. Once the patient has been enrolled and eligibility has been established, the order of the treatment visits will be randomized in blocks of 2 patients.
 
2. In Part 1, each patient will participate in 2 treatment visits: 1 with the iPhone-based BP using ZP4207 and 1 with the iPhone-based BP using Lilly glucagon in a randomized order. In Part 2, each patient will participate in 2 treatment visits: 1 with the iLet using ZP4207 and 1 with the iLet using Lilly glucagon in a randomized order. Up to 2 patients may participate in the trial per day.
 
3. The night before the visit, patients will place a Dexcom G4 CGM sensor in the abdominal skin and calibrate the sensor when prompted using the provided Nova StatStrip Xpress meter. Patients will be asked to arrive at the visit at least 1 hour in advance of the start of the BP having fasted since 12:00 AM the night before (treatment with simple carbohydrate of up to 30 g for a low is allowed). If the patient is not fasted, the visit will be rescheduled within the visit window. If BG is >250 mg/dL, the visit will be rescheduled within the visit window. If BG is <50 mg/dL, treatment with simple carbohydrate is allowed. If the patient experiences persistent hypoglycemia, the visit will be rescheduled within the visit window.
 
4. Visit 3 will take place at least 48 hours after screening (Visit 1) and no more than 30 days after screening (Visit 1).
 
5. There will be a 24-hour minimum washout between Visit 3 and Visit 4 and a maximum of 3 weeks between Visit 3 and Visit 4.
 
6. Visit 5 will take place 10 days ±3 days from Visit 4.
 
7. Visit 6 will take place 25 days ±4 days from Visit 4.
 
8. Height and physical examination will be measured at Visit 1 only.
 
9. Vital signs including body temperature and blood pressure will be obtained at visit start and visit end.
 
10. At visit start and visit end.
 
11. Urine HCG pregnancy test only for women of childbearing potential. The date of the last menstrual period in female patients will be obtained at Visit 1 only.
 
12. Test for FSH level only for postmenopausal women amenorrheic for less than 1 year.
 
13. If indicated by history.
 
14. Patients will be trained in the insertion and calibration of the Dexcom G4 sensor, diabetes management (e.g., basal insulin rate adjustment by insulin pump) during fasting prior to and between the treatment visits, and trial policies and procedures.
 
15. Collected at least hourly. If BG is <150 mg/dL, then sampling will be every 30 minutes. If BG is <100 mg/dL, then sampling will be every 20 minutes. If BG is <80 mg/dL, then sampling will be every 10 minutes.
 
16. Collected at least hourly. If BG is <150 mg/dL, more frequent samples for plasma ZP4207/glucagon may be drawn at the discretion of the Investigator.
 
17. Once the infusion sites have been placed but no drug has yet been administered.
 
18. Between approximately Hour 3 and Hour 4.
 
19. Between approximately Hour 6 and Hour 7.
 
20. Before the start of dosing.
 
ADA = anti-drug antibodies; BG = blood glucose; BP = bionic pancreas; CGM = continuous glucose monitor; ECG = electrocardiogram; FSH = follicle-stimulating hormone; HbA1c = hemoglobin A1c; HCG = human chorionic gonadotropin; VAS = visual analog scale.
						

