
3.2 Trial Endpoints

3.2.1 Primary Endpoint

The primary endpoint is the safety and tolerability of ZP4207 in the BP using either the iLet or the iPhone platform as assessed by

- Number and type of adverse events (AEs)
- Clinical laboratory measurements
- Vital signs
- 12-lead electrocardiograms (ECGs)
- Local tolerability and infusion site reactions as measured with the Draize scale
- Immunogenicity as measured by anti-drug antibodies (ADA)
- Pain as measured on a 10 cm visual analog scale (VAS)
- Nausea as measured on a 10 cm VAS

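### Treatment-emergent AEs are defined and tabulated by onset only, so an AE that worsens after dosing may be missed or counted under the first treatment alone

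*SAP*

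**What the plan says.** Section 3.2.1 puts "Number and type of adverse events (AEs" first among the components of the primary safety and tolerability endpoint. Section 4.6.1 then sets the rules for AEs:

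- Collection starts at consent: "All AEs from the time of signing the informed consent through trial completion will be recorded".
- Treatment-emergent status depends on onset: "treatment-emergent AEs (AEs with onset after [first] dosing at Visit 3 until the follow-up Visit 6".
- The only AE summary table is conditional ("If more than 20 treatment-emergent AEs") and "will be made by system organ class and treatment period at onset".
- Every AE is listed, whether or not it is treatment-emergent: "Individual AEs will be presented in a listing including relationship to trial product/device, severity, and treatment period at onset". SAEs have their own by-patient listing without that restriction. The listing of AEs leading to discontinuation is restricted to treatment-emergent ones.

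The footnotes to Table 1 in section 3.1 give the timing: "Visit 3 will take place at least 48 hours after screening (Visit 1) and no more than 30 days after screening (Visit 1", and "There will be a 24-hour minimum washout between Visit 3 and Visit 4 and a maximum of 3 weeks between Visit 3 and Visit 4".

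The SAP nowhere makes a rise in severity after dosing treatment-emergent, and nowhere says that a worsening is entered as a separate AE with its own onset date.

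**The concern.** AEs can be on file before any study drug is given, because recording begins at consent and first dosing follows 48 hours to 30 days after screening. If such an AE becomes more severe on drug, the worsening is part of tolerability, yet an onset-only definition does not recognise it.

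The cross-over adds a second gap. With as little as 24 hours between treatment visits, an event from period 1 can still be present at Visit 4. If it then worsens on the second drug, classification by period at onset leaves it with the first.

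At stake is the tabulated count for one component of the primary endpoint, and the completeness of the discontinuation listing. The individual record of the event is not at risk.

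**Working it through.** The plan gives no figure to reproduce, so the check applies the rules of section 4.6.1 to the possible event histories. It assumes that a worsening stays inside its original AE record.

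| Event history | Treatment-emergent? | Counted in the table | Adds to the trigger | In the discontinuation listing if it led to discontinuation |
|---|---|---|---|---|
| (a) Starts between consent and first dosing, worse after dosing | No | Not at all | No | No |
| (b) Starts in period 1, still present at Visit 4, worse after Visit 4 dosing | Yes | Once, under period 1 | Yes, once | Yes |
| (c) Starts after Visit 4 dosing | Yes | Once, under period 2 | Yes, once | Yes |

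In (a) the change on drug disappears from every treatment-emergent output. In (b) the event is counted, but nothing appears against the drug on which it worsened. History (c) is handled correctly and is shown for contrast.

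**If the recording rule is different.** If a worsening opens a new record dated at the worsening, (a) gains a record with onset after dosing and (b) gains one with onset in period 2. Both are then captured by the present wording. The result therefore turns on a rule that the SAP does not state.

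**Trigger.** The table needs more than 20 treatment-emergent AEs. Take 20 new-onset AEs and one of type (a):

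- Onset-only count: 20 + 0 = 20, which is not more than 20, so no table is produced.
- Count including the worsening: 20 + 1 = 21, so the table is produced.

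This matters only when the count lies at the threshold.

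**Incidence.** Section 4.1 keeps the two parts separate, and section 3.1 expects up to 10 completers in each. One patient is then 1/10 = 10 percentage points. If the upper figure of 24 randomized patients in section 5 split evenly (an assumption), each part would have 24/2 = 12 patients, and one patient would be 1/12 = 8.3 points. A shift of that size requires that the patient has no other AE in the same cell of the table. The SAP gives no rate of pre-dose AEs or of worsening, so an expected number cannot be calculated.

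**Direction.** Each omission of type (a) lowers the count for whichever drug was given when the event worsened. Each misplacement of type (b) lowers the count for whichever drug came second. The order is randomized and the rule is the same for both drugs, so the difference between ZP4207 and glucagon may move either way.

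**The case against.** The strongest reply is that the loss depends on a recording convention that a SAP normally leaves to the protocol's AE section or the eCRF instructions, neither of which is shown. Section 4.6.1 itself defines an AE broadly, so a worsening after dosing could be read as a new occurrence with its own onset. This stands as a condition on the finding. It does not remove it: the SAP supplies its own definition of treatment-emergent, and as written that definition works only under one of two recording conventions.

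Four stronger readings might be inferred, and the SAP does not support them:

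- *Signals of nausea or infusion site reaction are lost.* They are not. Table 1 schedules nausea, infusion site pain and infusion site reactions at visit start, hourly and at visit end. Sections 4.6.7 and 4.6.8 summarise them by treatment, with change from visit start for pain and nausea. All are primary endpoint components in their own right. Complaints such as headache have no such separate measure.
- *Events vanish from the report.* They do not. All AEs are listed with severity, and SAEs are listed separately. The limitation is that the AE listing, too, classifies by period at onset.
- *The rule favours ZP4207.* The direction of the comparison is not determined, and section 4.6 plans only a qualitative one.
- *Any pre-existing complaint is exposed.* Conditions present at screening are collected as history or concomitant illness, and a later worsening could then be reported as an AE with onset after dosing. The exposed group is AEs that start between consent and first dosing. Table 1 schedules AE review only from Visit 3, so few of these may be recorded.

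It is also fair that the summary table may never be produced, and that for the cross-over gap an event must outlast the interval between visits and then worsen.

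**Conclusion.** The point holds on a condition. Unless a worsening is entered as a new AE record, the onset-only rule leaves a worsened pre-dose AE out of the summary table, its trigger and the discontinuation listing, and it credits an AE that worsens on the second drug to the first drug only. The absolute count of on-drug events can be understated. No direction can be given for the comparison between drugs.

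The effect is probably small, because each treatment lasts one day, few events are exposed, the listings remain complete and the main local and nausea symptoms are measured separately. With about 10 patients per part, however, a single event can be visible in the table. This is a rule that gives a worse result than a readily available alternative. It is not an internal contradiction, and it does not undermine the safety assessment as a whole. It should be corrected because the cost is low.

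**What to change.** Amend section 4.6.1 before database lock, so that worsened events are not classified after results are seen:

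1. Define a treatment-emergent AE as one whose onset, or whose increase in severity over its pre-dose level, falls after first dosing at Visit 3 and up to Visit 6.
2. Tabulate by treatment period at onset or at worsening. Without this change, a worsened pre-dose AE would be treatment-emergent but would have no cell in the table.
3. Count an AE that worsens after Visit 4 dosing under the Visit 4 treatment as well, but only once in overall totals.
4. Use the same definition for the more-than-20 trigger and for the discontinuation listing.
5. If the eCRF enters a worsening as a new AE record, state this and say that the new record is the one counted.

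The cost is a few sentences of SAP text and a small programming rule. The rule needs either dated severity changes or new records for worsening, and the SAP does not show which of these the eCRF provides. No new visit or procedure is required.
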